
Study Design: This is a Phase 1 (postmarketing), single-center, 2-part, 3-period, 4-sequence, randomized, open-label, crossover design study. In Part A, subjects will receive 100-U bolus of U-500R by SC injection in 1 period and by CSII with basal infusion in another period (with sequence specified by the randomization schedule), prior to undergoing a euglycemic clamp procedure with a maximum duration of 24 hours. In Part B, subjects will be randomized to receive U-500R either TID or BID for 5 to 10 days prior to undergoing a 24-hour euglycemic clamp procedure.
	

Diagnosis and Main Criteria for Inclusion and Exclusion: High-dose insulin-treated (U-100, U-200, and/or U-300 insulin total daily dose [TDD] \geq150 U/day OR at least 1 dose $>$100 U as part of a multiple daily injection (MDI) regimen AND have TDD \leq3.0 U/kg) males or females with T2DM, \geq18 to $<$75 years old, with a body mass index of \geq27.0 kg/m², and HbA1c 7.5% to 11.5%, inclusive, at screening.
	

Test Product, Dosage, and Mode of Administration: Human regular U-500 insulin. Part A: 100 U, given as bolus once by single SC injection in 1 period and once by CSII in another period (following a 12-hour 4.25-U/hour infusion started 12 hours prior to the CSII bolus and continuing throughout the clamp). Part B: Individually tailored doses given either TID or BID by SC injection in the 5 to 10 days prior to and during Period 3. Randomized sequences will be followed for Parts A and B.
	

Comparator, Dose, and Mode of Administration: None.
	

Planned Duration of Treatment: Screening to occur up to 28 days prior to Period 1. Part A: 100 U bolus of U-500R will be administered once in each of 2 periods with 7 to 21 days between doses. Part B: U-500R will be administered TID or BID for up to 12 days. Each period will take approximately 2 days. Follow-up will occur 7 to 28 days after the end of the Period 3 clamp. Total maximum study duration approximately 13.5 weeks.

Criteria for Evaluation:

Safety: Safety data will include recording of adverse events, hypoglycemic events, self-monitored plasma glucose, clinical laboratory evaluations, vital signs, 12-lead electrocardiograms, body weight, and physical examinations.

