7.1.3. Part B (Study Period 3)

Following termination of the clamp procedure in Period 2, subjects will transition, as randomized, to TID or BID MDIs of U-500R. Human regular U-500 insulin will be self-administered by the subjects at home under telephone guidance from CRU staff during a telephone visit 2 to 3 days after the end of Period 2 (additional telephone or office visits may be added at the investigator's discretion). Initial U-500R doses will be based on each subject's insulin TDD prior to admission for Period 2, with titration for safety, if necessary, using the formulas given in Section 9.4. There will be 5 to 10 days between the end of Period 2 and the clamp in Period 3 (that is, dosing will begin on up to Day -10 and no later than Day -5 of Period 3) to allow steady state of the U-500R dosing regimen to be achieved. Mean self-monitored plasma glucose (SMPG) will be recorded from Day -5 until admission to the CRU.

Subjects will be admitted to the CRU on Day -1 of Period 3, prior to their pre-evening meal dose, which will be administered by CRU staff, and undergo fasting, PG stabilization, and a 24-hour euglycemic clamp as detailed in Section 7.1.2, with PK sampling as detailed in the Study Schedule ([Attachment 1](#)).

Following termination of the clamp procedure in Period 3 (Day 2), subjects will resume their prestudy insulin treatment regime. Discharge from the CRU will be subject to the same postclamp safety assessments as detailed in Section 7.1.2 and Section 10.4.1. Follow-up will occur 7 to 28 days after the end of Period 3 when safety procedures will be conducted and insulin use and dose will be recorded as detailed in the Study Schedule ([Attachment 1](#)).

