9.1. Treatment Materials and Supplies

This study involves a comparison of a 100-U bolus of U-500R administered by single SC injection versus administration via CSII and evaluation of U-500R administered SC TID and BID. [Table IBHG.9.1](#) shows the treatment regimens.

Table IBHG.9.1. Investigational Product Regimens

Regimen	Dose	Administration route	Time of administration
Part A	U-500R SC bolus	100-U	Single SC injection Prior to initiation of euglycemic clamp
	U-500R basal infusion plus U-500R CSII bolus	4.25 U/h basal and 100-U bolus	CSII 12 hour infusion of 4.25 U/h U-500R prior to 100-U bolus dose and initiation of euglycemic clamp (with continued 4.25-U/h U-500R infusion)
	U-500R TID	Per titration algorithm (TID, injectable solution)	Multiple daily SC injection Recommended 07:00, 12:00, and 18:00 hours, approximately 30 minutes prior to morning meal, midday meal, and evening meal, respectively ^a
Part B	U-500R BID	Per titration algorithm (BID, injectable solution)	Multiple daily SC injection Recommended 07:00 and 18:00 hours, approximately 30 minutes prior to morning meal and evening meal, respectively ^a

Abbreviations: BID = twice daily; CSII = continuous subcutaneous insulin infusion; SC = subcutaneous;

TID = thrice daily; U-500R = human regular U-500 insulin.

^a If a meal is skipped, insulin dose should be reduced by 50%.

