9.4. Dose Conversion from Prestudy Insulin in Part B

Subjects will record their insulin doses throughout the study. Baseline U-100, U-200, and/or U-300 insulin TDD will be defined as the highest TDD recorded in the 3 days prior to Period 2. All U-100, U-200, and/or U-300 insulin therapy will be discontinued upon initiation of study drug, but permitted prestudy AHA therapy should continue to be taken at prestudy doses, except on clamp assessment days. For all subjects with HbA1c >8.0% at screening, initial U-500R TDD will be the same (in units) as U-100, U-200, and/or U-300 insulin TDD at screening.

For all subjects with baseline HbA1c ≤8.0% at screening, initial U-500R TDD dose will be reduced by 20% from the U-100, U-200, and/or U-300 insulin TDD at screening.

Initial TID dosing will use a 40:30:30 proportion of calculated U-500R TDD for the respective pre-meal doses at 07:00 hours, 12:00 hours, and 18:00 hours, approximately 30 minutes prior to the morning meal, midday meal, and evening meal, respectively.

Initial BID dosing will use a 60:40 proportion of calculated U-500R TDD for the respective pre-meal doses at 07:00 hours and 18:00 hours, approximately 30 minutes prior to the morning meal and evening meal, respectively.

During dose conversion, bolus doses will be rounded down to the nearest 5 U as was done in Study B5K-US-IBHC (Hood et al. 2015). If subjects are using 0.5-mL U-100 insulin syringes, this will be to the closest unit marking (0.01 mL) on the syringe; for those using 1.0-mL U-100 insulin syringes, this will be half way between unit markings (0.02 mL).

Subjects will record SMPG throughout Period 3. During telephone visits (conducted 2 days after the end of Period 2 at a minimum) the investigator or designee will titrate subjects' U-500R dose for each meal according to the algorithms presented in [Table IBHG.9.2](#).

During dose titration (as opposed to initial dosage conversion), conventional rounding to the nearest 5 U will be applied, so that, for instance, values between 120.1 and 122.4 would be rounded down to 120 U while values between 122.5 and 124.9 would be rounded up to 125 U.

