Subjects should perform a 03:00 hours SMPG within 48 hours of any dose increase and should telephone the CRU the next morning if their 03:00 hours SMPG value is ≤70 mg/dL (≤3.9 mmol/L). The investigator may deviate from the algorithms, if deemed necessary, for the safety or well-being of the subject (for example due to illness, unusual SMPG patterns, or other safety concerns). Deviations from the algorithm should be discussed with Lilly, in advance if possible without compromising subject safety.

In the event of a subject reporting a severe hypoglycemic episode or any SMPG value is <50 mg/dL (<2.8 mmol/L), the investigator will make appropriate insulin adjustment per his/her judgment (this may be a 15% reduction in the appropriate U-500R mealtime dosage).

If a meal is skipped during the treatment period, the U-500R dose should be reduced by 50%.

Table IBHG.9.2. TID and BID Dosing Algorithms for U-500R Using Plasma-Equivalent Glucose Values

Algorithm	Insulin Dose to Adjust	Plasma-Equivalent Glucose Value	Value (mg/dL)	Action
TID Initial Dose Proportion 40:30:30	Pre-morning meal	Median pre-midday meal	≤70	Reduce dose by 10%
			71-130	No change in dose
			131-180	Increase dose by 5%
			181-220	Increase dose by 10%
			>220	Increase dose by 15%
	Pre-midday meal	Median pre-evening meal SMPG	≤70	Reduce dose by 10%
			71-130	No change in dose
			131-180	Increase dose by 5%
			181-220	Increase dose by 10%
			>220	Increase dose by 15%
BID Initial Dose Proportion 60:40	Pre-morning meal	Median pre-morning meal, median bedtime, or 03:00 hours SMPG	≤70	Reduce dose by 10%
			71-130	No change in dose
			131-180	Increase dose by 5%
			181-220	Increase dose by 10%
			>220	Increase dose by 15%
	Pre-evening meal	Median pre-morning meal, median bedtime, or 03:00 hours SMPG	≤70	Reduce dose by 10%
			71-130	No change in dose
			131-180	Increase dose by 5%
			181-220	Increase dose by 10%
			>220	Increase dose by 15%

Abbreviations: BID = twice daily; SMPG = self-monitored plasma glucose; TID = thrice daily.

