9.5. Specific Restrictions/Requirements

Prior to beginning the study, the subjects will complete informed consent and baseline tests.

Throughout the study, subjects may undergo medical assessments and review of compliance with restrictions before continuing in the study.

Meals/Diet – For all treatment periods, subjects will be fasted from approximately 12 hours prior to clamp initiation until after the clamp procedure is completed. Water can be consumed freely during this period.

When at home, subjects will be encouraged to maintain their body weight and consume their normal diets.

Alcohol – No alcohol will be allowed from at least 24 hours prior to clamp initiation and while resident in the CRU.

Smoking – Subjects will refrain from smoking, using electronic cigarettes, or using nicotine replacement therapy while resident in the CRU.

Exercise – Subjects will be encouraged to maintain their regular exercise; however, they should not undertake vigorous or prolonged exercise within 48 hours prior to each clamp day.

After dosing, and during the clamp procedure, subjects should remain recumbent or sitting in the CRU. Movement will be restricted to retain integrity of connections to infusion and study procedures.

Authorization to leave the CRU must be given by a physician.

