Attachment 1. Protocol IBHG Study Schedule

Study Schedule Protocol B5K-EW-IBHG

		Periods 1 and 2 ^a			Period 3					
		Days			Days				Follow-up	Comments
Procedure	Screening	-1	1	2	-10 ^b to -2	-1	1	2	7 to 28 days after discharge or early discontinuation	
Informed consent	X									
Subject admission to CRU		X				X				
U-100, U-200, and/or U-300 insulin dosing	X	X		X				X		U-100, U-200, and/or U-300 dosing on Day -1 of Period 1 and 2 to end ≥ 15 h prior to U-500R bolus dosing. Transition to U-100, U-200, and/or U-300 insulin after Period 3 is per investigator judgment.
Subject discharge from CRU				X				X		Subjects will remain at the CRU until BG is stable according to investigator judgment.
Recording of U-100, U-200, and/or U-300 insulin TDD	X	X		X				X		Subjects will record their U-100, U-200, and/or U-300 insulin TDD throughout the study apart from during dosing with U-500R.
Type and dose of insulin use recorded									X	

		Periods 1 and 2 ^a			Period 3					
	Screening	Days			Days				Follow-up	Comments
Procedure	Up to 28 days prior to Period 1	-1	1	2	-10 ^b to -2	-1	1	2	7 to 28 days after discharge or early discontinuation	
Telephone visit for U-500R dose titration					X					Telephone visit for review of SMPG 2 to 3 days after end of Period 2. Additional visits may be conducted at the investigator's discretion.
Recording of U-500R doses					X					
Start of 4.25-U/hour U-500R infusion		X								Infusion to start 12 hours prior to bolus administration by CSII and continue throughout the clamp procedures.
Bolus U-500R administration			X							
TID or BID administration of U-500R					X					Dosing will begin following Period 2 and will stop at the end of the Period 3 clamp procedure.
Height	X									
Weight	X	X			X				X	Body weight should be recorded on Day -1 of all study periods.

Procedure	Screening	Periods 1 and 2 ^a			Period 3				Follow-up	Comments	
		Days	Days	Follow-up							
Up to 28 days prior to Period 1	-1	1	2	-10 ^b to -2	-1	1	2	7 to 28 days after discharge or early discontinuation			
Vital signs (supine) (hours relative to bolus/morning dose)	X	-12 h (predose) ^d	Predose, 1, 2, 4, 8, 12, 16 h	24 h ^c				Predose, 1, 2, 4, 8, 12, 16 h	24 h	X	Supine blood pressure and/or pulse rate may be measured as clinically indicated. Additional vital signs may be measured during each study period, if warranted and agreed upon between Lilly and the investigator.

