Clinical laboratory tests	X	X (Period 1 only)								X	See Attachment 2 , Clinical Laboratory Tests, for details.
Pregnancy test	X	X				X				X	Serum pregnancy test will be performed at screening. Urine pregnancy test will be performed at every admission period and at poststudy, if applicable.
Physical exam	X										After screening, medical assessment only performed to include medical review and targeted examination, as appropriate.
12-lead ECG	X		Predose	24 h ^c				Predose	24 h	X	

	Screening	Periods 1 and 2 ^a			Period 3				Follow-up	Comments
		Days			Days					
Procedure	Up to 28 days prior to Period 1	-1	1	2	-10 ^b to -2	-1	1	2	7 to 28 days after discharge or early discontinuation	
SMPG					X					4-point SMPG to be conducted daily throughout the study, except whilst resident in the CRU. Mean SMPG for the 5 days prior to Period 3 will be collected in the eCRF.
Overnight PG stabilization		X				X				PG stabilized using an insulin lispro and/or glucose drip.
Euglycemic clamp			X				X			
Pharmacogenetic sample		X (predose)								Single sample for pharmacogenetic analysis taken on Day -1 of Period 1.
PK and C-peptide samples		-12, -8, -4 h	-0.5, 0 (predose), 0.5, 1, 2, 3, 4, 5, 6, 7, 8, 12, 16 h	24 h			-0.5, 0 (predose), 0.5, 1, 2, 3, 4, 5 (predose for TID), 6, 7, 9, 11 (predose), 12, 13, 15, 18 h	24 h		Sampling times are relative to the time of the start of study treatment morning bolus administration (0 h). Sampling times for Period 3 are relative to the time of breakfast (0 hr), lunch (5 hr) and dinner (11 hr).

Abbreviations: BG = blood glucose; BID = twice daily; CRU = clinical research unit; CSII = continuous subcutaneous insulin infusion; ECG = electrocardiogram; PG = plasma glucose; PK = pharmacokinetics; SMPG = self-monitored plasma glucose; TDD = total daily dose; TID = thrice daily; U-500R = human regular U-500 insulin.

- a There may be 7 to 21 days between bolus doses in Period 1 and Period 2.
- b There may be 5 to 10 days between the end of Period 2 and clamp initiation in Period 3 (Day 1), that is BID or TID dosing may begin on Day -10 through Day -5.
- c Clamp procedure in Periods 1 and 2 are of a maximum duration of 24 hours. Vital signs and ECGs will be conducted at the end of the clamp procedure.
- d CSII period only, taken prior to initiation of 12-hour U-500R infusion.

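### Does the skipped-meal rule halve the U-500R doses given during the fasted Part B clamp and so spoil the steady-state measurement?

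*Protocol*

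**What the plan says.** The rule appears twice in the protocol. Section 9.4 has "If a meal is skipped during the treatment period, the U-500R dose should be reduced by 50" percent. Footnote a to Table IBHG.9.1 in Section 9.1, attached to both Part B regimens, has "If a meal is skipped, insulin dose should be reduced by 50" percent.

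Section 9.5 sets the fast: "For all treatment periods, subjects will be fasted from approximately 12 hours prior to clamp initiation until after the clamp procedure is completed". Section 7.1.3 applies it to Part B, where subjects "undergo fasting, PG stabilization, and a 24-hour euglycemic clamp as detailed in Section 7.1.2".

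U-500R continues meanwhile. The Study Schedule (Attachment 1) says of TID or BID administration: "Dosing will begin following Period 2 and will stop at the end of the Period 3 clamp procedure". The Synopsis describes "Individually tailored doses given either TID or BID by SC injection in the 5 to 10 days prior to and during Period 3". Period 3 samples are timed from breakfast, lunch and dinner at 0, 5 and 11 hours, with predose samples at 0 h, 5 h (TID) and 11 h.

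The Part B primary objective (Section 6.1) concerns AUC(0-24), Cmax and Rmax at steady state. Sections 11.2.4.2 and 11.2.5.2 plan no formal analysis for Part B, only listings and summaries.

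**The concern.** Each clamp-day dose is timed as a pre-meal dose, yet no meal is eaten. Neither statement of the rule is limited to days at home or exempts the clamp. Section 9.5 uses the term treatment periods in a way that includes the clamp, which resembles the scope given in Section 9.4. Section 9.4 also writes a clamp-day exception for another drug class: "permitted prestudy AHA therapy should continue to be taken at prestudy doses, except on clamp assessment days". It writes none for the skipped-meal rule.

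Read literally, every dose in the measurement window would be half of what the subject had been taking. The profile would then show a step down from steady state, although the results are meant to describe steady state and to check model predictions (Section 5.2). If some subjects were halved and others not, the summaries would mix two regimens. With no inference planned, those summaries are the whole Part B result.

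**Working it through.** The plan gives no figure for this point. Its only design calculation is the Part A precision statement for tmax, which does not involve Part B doses. The check therefore has two parts: how large the effect would be under the literal reading, and whether the text supports that reading.

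**Which doses are involved.** The recommended dose times are 07:00, 12:00 and 18:00 (Table IBHG.9.1). They match the 0, 5 and 11 h sampling marks: 07:00 + 5 h = 12:00, and 07:00 + 11 h = 18:00. A 12-hour fast before a 07:00 clamp starts at 19:00, after an evening meal taken about 30 minutes after the 18:00 dose on Day -1. The question is thus confined to the doses at 0, 5 (TID only) and 11 h.

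**Dose arithmetic, with no kinetic assumption.** The example subjects in Sections 9.4.1 and 9.4.2 take 300 U a day.
- TID: 120 + 90 + 90 = 300 U, or 60 + 45 + 45 = 150 U if halved.
- BID: 180 + 120 = 300 U, or 90 + 60 = 150 U if halved.

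**Exposure if all clamp-day doses were halved.** Inputs from the protocol are the 40:30:30 split at 0/5/11 h and the 60:40 split at 0/11 h. Assumptions not in the documents are linear one-compartment kinetics, elimination half-life 1 to 4 h and absorption half-life 3 to 8 h. Per unit dose,

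C(t) ∝ [ka/(ka − ke)] × [exp(−ke·t) − exp(−ka·t)],

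summed over 10 prior full-dose days and the clamp day. If f is the share of the steady-state AUC(0-24) that comes from doses given before the clamp day, then

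AUC ratio = 0.5 + 0.5 × f.

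Over the grid f runs from 0.030 to 0.361, so the ratio runs from 0.5 + 0.5 × 0.030 = 0.515 to 0.5 + 0.5 × 0.361 = 0.681.

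| Half-lives (elimination / absorption) | AUC ratio, TID / BID | Cmax ratio, TID / BID | C(24 h)/C(0 h), TID / BID |
|---|---|---|---|
| 2 h / 3 h | 0.526 / 0.529 | 0.521 / 0.547 | 0.50 / 0.50 |
| 2 h / 5 h | 0.570 / 0.571 | 0.556 / 0.611 | 0.52 / 0.52 |
| 2 h / 8 h | 0.636 / 0.636 | 0.619 / 0.694 | 0.56 / 0.56 |
| Range over the whole grid | 0.515 to 0.681 | 0.511 to 0.759 | 0.50 to 0.58 |

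With unchanged doses every ratio is 1.00. Rmax cannot be computed from the documents. The effect would be large, so the matter turns on the text.

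**What the text supports.**
- *Placement.* In Section 9.4 the rule follows instructions on 03:00 self-monitoring, telephoning the unit and subjects reporting hypoglycemia. In Table IBHG.9.1 it qualifies recommended clock times before meals. Both are settings in which subjects dose themselves at home.
- *Vocabulary.* Sections 7.1.2, 7.1.3 and 9.5 describe clamp abstention as fasting. Skipping a meal is mentioned only in the rule itself.
- *Clamp-day changes.* Where the protocol wants a drug handled differently on clamp days, it says so, as for antihyperglycemic agents in Sections 9.4 and 9.7. It states no such change for U-500R.
- *Continuity.* The Synopsis gives one dose description for the days before and during Period 3, and the Study Schedule ends dosing with the clamp.
- *Meal labels.* SAP Section 9.3.1 calls the meal periods assumed and places them at steady state. Breakfast, lunch and dinner are therefore nominal time marks.

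No passage states a clamp-day dose that another passage contradicts. The documents are silent on the point, and the indirect evidence runs one way.

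**The case for a change.** The strongest case for a change is that the at-home reading is nowhere written down. The scope wording in Section 9.4 can be read to cover the clamp, and the exception for antihyperglycemic agents shows that the authors could exempt clamp days when they chose to. Unit staff give every clamp-day dose and would benefit from one explicit line. The investigator's freedom to depart from the algorithms is for subject safety or well-being and does not define the clamp-day regimen. Recording is also less than complete on its face: Section 9.2 names the time of each dose for the eCRF, and the schedule row for recording U-500R doses is marked only for Days -10 to -2.

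Part of this stands. The gap is real, and a cross-referenced sentence would be harmless; its clinical content would be the sponsor's decision. The recording argument is weaker. Section 7.1.4 asks for all insulin doses in the diary, Section 9.4 has doses recorded throughout the study, and SAP Section 9.5.6 lists the change in total daily dose to Period 3 U-500R in units and units/kg, which needs amounts. The schedule marks are poor evidence in either direction: the administration row is also marked only for Days -10 to -2, although its comment carries dosing to the end of the clamp. None of these entries names the clamp day, so a small uncertainty remains.

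**Conclusion.** No change to the plan is needed. The documents do not say whether a planned fast counts as a skipped meal, but the objective, the dose description, the dosing schedule and the SAP all read as a regimen that continues through the clamp. This is a judgment about what the text conveys and takes no view on which dose is clinically right.

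At a single center, with one unit's staff giving the clamp-day doses, divergent practice between sites cannot arise, and on the natural reading the descriptive Part B results mean what the objective says. No hypothesis test, error rate, sample size or Part A result is touched. Reserving the steady-state label for subjects whose clamp-day doses match their earlier regimen would matter only under the less natural reading.

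The AUC(0-24) range of about 52-68% and the Cmax range of about 51-76% depend on assumed half-lives and on that same reading, so they are illustrative. The conclusion would change only if there were evidence that clamp-day doses were to be halved, and the documents contain none.

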9.4.1. TID Treatment Group Titrations

Subjects in the TID treatment group will have their insulin doses adjusted at a telephone visit 2 to 3 days after the end of Period 2 (at a minimum, additional telephone or office visits may be added for safety as necessary) by the investigator or site designee according to the TID titration algorithm (Table IBHG.9.2).

The U-500R doses will be changed according to corresponding median plasma-equivalent glucose readings from the most recent 3 values at respective times (also see examples below) prior to the telephone or office visit or for any add-on telephone calls or office visits. If even

1 SMPG reading for a given time point is ≤ 70 mg/dL (≤ 3.9 mmol/L), no dosage increase will be applied to the corresponding dose. These adjustments will be applied only to the 2 of the 3 doses (pre-morning meal, pre-midday meal, pre-evening meal) that most need adjustment (that is, the ones with the most out-of-range corresponding median plasma-equivalent glucose readings) at each study visit/interaction.

For subjects receiving U-500R TID, median pre-morning meal and bedtime SMPG values and 03:00 hours SMPG values (if performed) will inform adjustment of the pre-evening meal U-500R insulin dose. When these 3 sets of values provide conflicting guidance, the investigator should base the dose adjustment on the lowest of these results, and prioritize adjustments for hypoglycemic readings ≤ 70 mg/dL (≤ 3.9 mmol/L) over dosage increases.

In all instances, the 10% dosage reduction for values ≤ 70 mg/dL (≤ 3.9 mmol/L) and negation of respective dosage increases for single pre-meal or bedtime hypoglycemic readings should be prioritized over other titration options.

Example 1

A subject assigned to the TID treatment group is taking 300 U TDD with a pre-morning meal dose of 120 U, pre-midday meal dose of 90 U and a pre-evening meal dose of 90 U.

Over the last 3 days, the subject's SMPG values were:

Date	Day 1	Day 2	Day 3
SMPG pre-morning meal, mg/dL (mmol/L)	102 (5.7)	110 (6.1)	135 (7.5)
SMPG pre-midday meal, mg/dL (mmol/L)	163 (9.1)	180 (10.0)	200 (11.1)
SMPG pre-evening meal, mg/dL (mmol/L)	240 (13.3)	221 (12.3)	238 (13.2)
SMPG at bedtime, mg/dL (mmol/L)	130 (7.2)	160 (8.9)	125 (6.9)
SMPG at 03:00 hours, mg/dL (mmol/L)			92 (5.1)

Abbreviation: SMPG = self-monitored plasma glucose.

The 2 doses that most need adjustment are pre-midday meal and pre-morning meal because the median glucose values at pre-evening meal and pre-midday meal are the most outside of the target range. The subject's median pre-evening meal SMPG is 238 mg/dL (13.2 mmol/L); therefore, the pre-midday meal dose should be increased by 15% to 103.5 U, rounded up to 105 U. The subject's median pre-midday meal SMPG is 180 mg/dL (10.0 mmol/L); therefore, the pre-morning meal dose should be increased by 5% to 126 U, rounded down to 125 U.

Example 2:

A subject assigned to the TID treatment group is taking 210 U TDD with a pre-morning meal dose of 90 U, pre-midday meal dose of 60 U, and pre-evening meal dose of 60 U.

Over the last 3 days, the subject's SMPG values were:

Date	Day 1	Day 2	Day 3
SMPG pre-morning meal, mg/dL (mmol/L)	160 (8.9)	145 (8.1)	110 (6.1)
SMPG pre-midday meal, mg/dL (mmol/L)	181 (10.1)	185 (10.3)	120 (6.7)
SMPG pre-evening meal, mg/dL (mmol/L)	140 (7.8)	120 (6.7)	170 (9.4)
SMPG at bedtime, mg/dL (mmol/L)	68 (3.8)	120 (6.7)	140 (7.8)
SMPG at 03:00 hours, mg/dL (mmol/L)		60 (3.3)	

Abbreviation: SMPG = self-monitored plasma glucose.

The 2 doses that appear to most need adjustment are pre-morning meal and pre-evening meal because the median glucose values at pre-midday meal and pre-morning meal are the most outside of the target range (181 and 145 mg/dL (10.1 and 8.1 mmol/L), respectively). However, due to the 03:00 hours SMPG being \leq 70 mg/dL (\leq 3.9 mmol/L), the first prioritized dose change would be the subject's pre-evening meal dose which should be reduced by 10% to 54 U, rounded up to 55 U. After that first dose adjustment, the next adjustment most needed would be a 10% increase in the subject's pre-morning meal dose to 99 U, rounded up to 100 U on the basis of the pre-midday median glucose value of 181 mg/dL (10.1 mmol/L). Since only 2 of 3 TID doses can be adjusted, no change would be applied to the pre-midday meal dose.

Example 3:

A subject assigned to the TID treatment group is taking 300 U TDD with a pre-morning meal dose of 120 U, pre-midday meal dose of 90 U, and pre-evening meal dose of 90 U.

Over the last 4 days, the subject's SMPG values were:

Date	Day 1	Day 2	Day 3	Day 4
SMPG pre-morning meal, mg/dL (mmol/L)	66 (3.7)	148 (8.2)		160 (8.9)
SMPG pre-midday meal, mg/dL (mmol/L)	120 (6.7)	142 (7.9)	180 (10.0)	
SMPG pre-evening meal, mg/dL (mmol/L)	68 (3.8)	64 (3.6)		135 (7.5)
SMPG at bedtime, mg/dL (mmol/L)	102 (5.7)	135 (7.5)		165 (9.2)
SMPG at 03:00 hours, mg/dL (mmol/L)		100 (5.6)		

Abbreviation: SMPG = self-monitored plasma glucose.

The investigator should consider changing only the 2 doses that most need adjustment. In this instance, the 2 doses that appear to most need adjustment are pre-evening meal and pre-morning meal because the median glucose values at pre-morning meal and pre-evening meal are the most outside of the target range. The median pre-morning meal SMPG (148 mg/dL [8.2 mmol/L]) is within the range of 131 to 180 mg/dL (7.3 to 10.0 mmol/L) calling for a 5% dose increase of pre-evening meal dosage. However, the unexplained hypoglycemia (66 mg/dL [3.7 mmol/L]) takes precedence and accordingly, there should be no upward evening meal dosage adjustment. The median of the last 3 readings for pre-evening meal SMPG (68 mg/dL [3.8 mmol/L]) is \leq 70 mg/dL (\leq 3.9 mmol/L); therefore, the investigator would reduce the pre-midday meal dose by 10% to 81 U, which is rounded to 80 U, the nearest 5 U.

9.4.2. *BID Treatment Group Titrations*

Subjects in the BID treatment group will have their insulin dosages adjusted at each study visit (office and telephone or for add-on visits) by the investigator or site designee according to the BID titration algorithm ([Table IBHG.9.2](#)).

Human regular U-500 insulin doses will be changed according to corresponding median plasma-equivalent glucose readings from the most recent 3 values at respective times (also see examples below) prior to the scheduled telephone or office visit or for any add-on visits. If even 1 of the SMPG readings for a given time point is ≤ 70 mg/dL (≤ 3.9 mmol/L), no dosage increase will be applied to the corresponding dose. These adjustments will be applied to both doses as indicated (pre-morning meal and pre-evening meal) at each study visit/interaction.

For subjects receiving U-500R BID, median pre-morning and bedtime SMPG values and 03:00 hours SMPG values (if performed) will inform adjustment of the pre-evening meal U-500R insulin dose, and both median pre-evening meal and pre-midday meal SMPG values will inform adjustment of the pre-morning meal U-500R insulin dose. When these sets of values provide conflicting guidance, investigators should base the dose adjustment on the lowest of these results, and prioritize adjustments for hypoglycemic readings ≤ 70 mg/dL (≤ 3.9 mmol/L) over dosage increases.

In all instances, the 10% dosage reduction for median pre-meal/bedtime values or single 03:00 hours glucose values ≤ 70 mg/dL (≤ 3.9 mmol/L) and negation of respective dosage increases for single pre-meal or bedtime hypoglycemic readings should be prioritized over other titration options.

Example 1:

A subject assigned to the BID treatment group is taking 300 U TDD, with a pre-morning meal dose of 180 U and a pre-evening meal dose of 120 U.

Over the last 4 days, the subject's SMPG values were:

Date	Day 1	Day 2	Day 3	Day 4
SMPG pre-morning meal, mg/dL (mmol/L)	180 (10.0)	160 (8.9)	200 (11.1)	
SMPG pre-midday meal, mg/dL (mmol/L)		120 (6.7)	170 (9.4)	132 (7.3)
SMPG pre-evening meal, mg/dL (mmol/L)	200 (11.1)		225 (12.5)	260 (14.4)
SMPG at bedtime, mg/dL (mmol/L)	142 (7.9)		128 (7.1)	110 (6.1)
SMPG at 03:00 hours, mg/dL (mmol/L)	101 (5.6)			

Abbreviation: SMPG = self-monitored plasma glucose

The median pre-evening meal SMPG value is 225 mg/dL (12.5 mmol/L); therefore, the subject's pre-morning meal dose should be increased by 15% to 207 U, rounded down to 205 U. The median pre-morning meal SMPG value is 180 mg/dL (10.0 mmol/L); therefore, the subject's pre-evening meal dose should be increased by 5% to 126 U, rounded down to 125 U.

Example 2:

A subject assigned to the BID treatment group is taking 250 U TDD, with a pre-morning meal dose of 150 U and a pre-evening meal dose of 100 U.

Over the last 4 days, the subject's SMPG values were:

Date	Day 1	Day 2	Day 3	Day 4
SMPG pre-morning meal, mg/dL (mmol/L)		138 (7.7)	130 (7.2)	110 (6.1)
SMPG pre-midday meal, mg/dL (mmol/L)	80 (4.4)	71 (3.9)	58 (3.2)	
SMPG pre-evening meal, mg/dL (mmol/L)	160 (8.9)		200 (11.1)	182 (10.1)
SMPG at bedtime, mg/dL (mmol/L)	140 (7.8)		132 (7.3)	110 (6.1)
SMPG at 03:00 hours, mg/dL (mmol/L)		142 (7.9)		

Abbreviation: SMPG = self-monitored plasma glucose.

The median pre-evening meal SMPG is 182 mg/dL (10.1 mmol/L); thus, the subject's pre-morning meal dose would normally be increased by 10%. However, there is a single pre-midday meal hypoglycemic reading (58 mg/dL [3.2 mmol/L]); therefore, the pre-morning meal dose should not be increased. The median pre-morning meal SMPG value is 130 mg/dL (7.2 mmol/L); therefore, the subject's pre-evening meal dose should not change.

Example 3:

A subject assigned to the BID treatment group is taking 275 U TDD with a pre-morning meal dose of 165 U and a pre-evening meal dose of 110 U.

Over the last 3 days, the subject's SMPG values were:

Date	Day 1	Day 2	Day 3
SMPG pre-morning meal, mg/dL (mmol/L)	66 (3.7)	141 (7.8)	160 (8.9)
SMPG pre-midday meal, mg/dL (mmol/L)	131 (7.3)	128 (7.1)	105 (5.8)
SMPG pre-evening meal, mg/dL (mmol/L)	66 (3.7)	70 (3.9)	110 (6.1)
SMPG at bedtime, mg/dL (mmol/L)	100 (5.6)	112 (6.2)	108 (6.0)
SMPG at 03:00 hours, mg/dL (mmol/L)	70 (3.9)		

Abbreviation: SMPG = self-monitored plasma glucose.

The median pre-evening meal SMPG is 70 mg/dL (3.9 mmol/L); therefore, the pre-morning meal dose should be reduced by 10% to 148.5 U, rounded up to 150 U. The median pre-morning meal SMPG is 141 mg/dL (7.8 mmol/L), but the subject's pre-evening meal dose should not be titrated upward due to the 03:00 hours value being \leq 70 mg/dL (\leq 3.9 mmol/L) (70 mg/dL [3.9 mmol/L]) which also necessitates a 10% reduction, in the pre-evening meal dose to 99 U, rounded up to 100 U.

